7.3.2 Whole exome sequencing and data analysis

The saliva collection kits can be returned via regular mail and will be stored at room temperature (15-30°C) until analysis.

The collected saliva samples will be sent to GenomeScan (an ISO/IEC 17025 accredited laboratory). The samples will only contain the study specific number of the participant. GenomeScan will do the DNA isolation. DNA sequencing will be done using the Agilent SureSelect Human All Exon V7 kit, using Illumina

NovaSeq6000 sequencing, Paired-End, 150 bp. Per sample we will obtain ~12 Gb, 40 million Paired-End reads.

In a NEN-EN-ISO 15189 accredited genome diagnostic center existing bio-informatic pipelines and databases will be used. Sequenced reads will be mapped to the Genome Reference Consortium Human Build 37 (GRCh37 or hg19) reference genome. Variants are classified according the guidelines as established by the American College of Medical Genetics and Genomics and the Association for Molecular Pathology guideline (33), similar to the approach in our Genetics first – primary immunodeficiencies study (34, 35).

We will make use of publicly available reference exome data sets (including GnomAD database, GoNL database) to determine the frequency of genetic variants in reference populations (36). We will include only protein-altering variation with a presumed high impact on protein function, including protein-truncation (stop or frameshift mutations) or disturbance of canonical splice-sites. In-frame insertions/deletions and missense mutations will be scored, and variants with a 'likely' estimated impact on protein functioning (CADD>15) will be included in the analysis (37, 38).

Class	Description	Probability of being Pathogenic
5	Definitely Pathogenic	>0.99
4	Likely Pathogenic	0.95–0.99
3	Uncertain	0.05–0.949
2	Likely Not Pathogenic or of Little Clinical Significance	0.001–0.049
1	Not Pathogenic or of No Clinical Significance	<0.001

Data collection

Clinical data:

- Clinical data of the MIS-C and post-covid condition patients has already been collected in the existing studies. We will ask consent of the participants to use this data to be able to compare genetic and clinical data.
- For the 'exposed' controls we will need to verify that prior SARS-CoV-2 infection(s) was/were uncomplicated. This needs to be the case in order for the subject to be eligible for inclusion in the present study. This we will verify in the introductory phone call. Also, to assess whether cases and controls have different genetic backgrounds, we will ask what the birth place is of the parents and grandparents of the subject (this is important for the interpretation of rare genetic variants). Age (in years) and gender will be collected from the cases since MIS-C and post-COVID condition occur mainly in school-aged children. Information on prior infections, age and birthplace of (grand)parents of the healthy 'exposed' controls will be entered in Castor EDC.

Genetic data:

- GenomeScan will provide us with FASTQ files containing the sequencing reads.

Reporting of individual genetic results to the participant

Cases (MIS-C or 'post-COVID condition'):

We will do individual genetic analyses of whole exome sequencing results of genes associated with inborn errors of immunity. Cases with class 4 or 5 variants in these IEI genes (also taking into account the mode of inheritance, e.g. autosomal recessive, X-linked etc.) have a likely diagnosis of an inborn error of immunity. Since this can have clinical implications, we will refer cases with a likely diagnosis of an IEI to a clinical geneticist for counseling. Genetic results will be reported back according to the VKGN consensus-based guideline (39):

Cases (MIS-C or 'post-COVID condition'):

1. There is a diagnosis of IEI which according to current knowledge explains why the child had MIS-C or post-COVID condition. This we will report back to the participant regardless of whether the diagnosis of IEI will lead to a change in treatment or follow-up.
2. There is a diagnosis of a genetic disease, but according to current knowledge it does not explain why the child had MIS-C or post-COVID condition (incidental finding). We will report incidental findings back to the participant, if:
 - according to current knowledge the diagnosis would lead to a change in management (treatment or follow-up) of the participant during childhood (until the age of 16 years)
 - according to current knowledge the diagnosis would lead to a change in management (treatment or follow-up) of the participant after the age of 16 years. Participants can choose to 'opt out' to receive this information.
 - according to current knowledge the diagnosis does **not** lead to change in management (treatment or follow-up): we will **not** report these findings. Participants older than 16 years of age can choose to 'opt in' to receive these results.
 - according to current knowledge there is no genetic diagnosis in the participant, but the chance that potential future off-spring of the participant is born with the condition is higher than 25%. Participants can choose to 'opt out' to receive this information.

Controls

- In the case-control part of the study, data on genetic variants are analyzed at 'group level' and not traced back to the individual participants. Therefore, controls (healthy, SARS-CoV-2 exposed children) will not receive feedback on their own genetic data.

Reporting of overall results

Eventually, overall results will be published on our website www.covidkids.nl and in scientific journals.

7.4 Withdrawal of individual subjects

Subjects can leave the study at any time for any reason if they wish to do so without any consequences.

7.5 Replacement of individual subjects after withdrawal

When an individual withdraws from the study, we will continue inviting other possible participants until we reach the number of participants that are needed in this study.

7.6 Follow-up of subjects withdrawn from treatment

Not applicable

7.7 Premature termination of the study

The study will be prematurely terminated in case of problems regarding the inclusion or participation of patients. Also, the study will be terminated if it is temporarily suspended for reasons of subjects' safety and the accredited METC gives a negative decision after assessing the reasons that led to the temporary suspension.

8. SAFETY REPORTING

8.1 Temporary halt for reasons of subject safety

In accordance to section 10, subsection 4, of the WMO, the sponsor will suspend the study if there is sufficient ground that continuation of the study will jeopardize subject health or safety. The sponsor will notify the accredited METC without undue delay of a temporary halt including the reason for such an action. The study will be suspended pending a further positive decision by the accredited METC. The investigator will take care that all subjects are kept informed.

8.2 AEs, SAEs and SUSARs

8.2.1 Adverse events (AEs)

Adverse events are defined as any undesirable experience occurring to a subject during the study, whether or not considered related to the study procedure. For this study, we will not register adverse events, since the study procedure is a one-time very low risk procedure, for which we do not expect study related adverse events to occur.

8.2.2 Serious adverse events (SAEs)

A serious adverse event is any untoward medical occurrence or effect that

- results in death;
- is life threatening (at the time of the event);
- requires hospitalization or prolongation of existing inpatients' hospitalization;
- results in persistent or significant disability or incapacity;
- is a congenital anomaly or birth defect; or
- any other important medical event that did not result in any of the outcomes listed above due to medical or surgical intervention but could have been based upon appropriate judgement by the investigator.

An elective hospital admission will not be considered as a serious adverse event.

Only study related SAE's will be reported immediately. This means all SAE's related to participation in this study protocol, meaning from the saliva collection, will be reported. All other SAE's will not be reported, since the study procedure is considered to be of very low risk.

The sponsor will report these SAEs through the web portal ToetsingOnline to the accredited METC that approved the protocol, within 7 days of first knowledge for SAEs that result in death or are life threatening followed by a period of maximum of 8 days to complete the initial preliminary report. All other SAEs will be reported within a period of maximum 15 days after the sponsor has first knowledge of the serious adverse events.

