10.4 Benefits and risks assessment, group relatedness

Children with MIS-C or 'post-COVID condition' may benefit from this study since they might receive a genetic diagnosis that explains why they have had a complicated clinical course following infection with SARS-CoV-2. This may benefit them by ensuring they will receive proper care targeted at the underlying condition. At the same time, there is a risk that the genetic diagnosis does not have therapeutic consequences. This may be a burden for the participant/family. Also, a genetic diagnosis in the participant may have implications for other family members.

Controls do not benefit personally from study participation.

The procedure to collect the DNA (saliva collection) will have negligible risks and minimal burden .

This study can only be performed in minors, as it will provide age-specific data that cannot be obtained otherwise. MIS-C is a condition that mainly occurs in children (MIS-A in adults is very rare).

Regarding children with post-COVID condition: Since the immunological and clinical response to SARS-CoV-2 is markedly different between adults and children, results obtained in studies on post-COVID condition or 'long COVID' in adults do not automatically apply to children with this condition.

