10.5 Compensation for injury

The sponsor/investigator has a liability insurance which is in accordance with article 7 of the WMO. We request dispensation by the METC for the statutory obligation to provide insurance for damage to research subjects, because participating in this study is without risks.

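### Returning genetic results to cases is a study procedure with a risk named in section 10.4, yet section 8.2.2 limits reportable SAEs to saliva collection and section 10.5 seeks an insurance dispensation on the ground that there is no risk

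*Protocol*

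**What the plan says.** **Return of results (7.3.2).** Cases with class 4 or 5 variants in IEI genes, with a fitting mode of inheritance, are referred to a clinical geneticist for counselling. A diagnosis that explains the illness is reported back whether or not it changes management. Certain incidental findings are also returned, with opt-in or opt-out choices for some. Controls receive no individual results.

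**Risk (10.4).** For cases the protocol states that "there is a risk that the genetic diagnosis does not have therapeutic consequences" and adds: "This may be a burden for the participant/family". It also mentions implications for relatives. Saliva collection is rated as carrying negligible risk.

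**Safety reporting (8.2).** On AEs: "For this study, we will not register adverse events, since the study procedure is a one-time very low risk procedure". On SAEs, those "related to participation in this study protocol, meaning from the saliva collection, will be reported". Then: "All other SAE's will not be reported, since the study procedure is considered to be of very low risk". Under 8.4, SAE reporting runs to the end of the study, which 11.5 sets at receipt of the DNA results of the last included participant.

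**Risk analysis (chapter 12).** Only the sponge and the saliva kits are considered.

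**Insurance (10.5).** The sponsor has liability insurance and asks to be released from the separate obligation to insure damage to subjects, "because participating in this study is without risks".

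**The concern.** The study does two things to a case: it collects saliva, and it may return a genetic result. Section 10.4 attaches a named risk to the second and calls the risk of the first negligible. The safety chapter and the structured risk analysis address only the first.

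This is a stated rule and not a detail left for another document. If an investigator judged that an SAE had been caused by disclosure of a result, that event would be study-related in the ordinary sense but excluded by the definition in 8.2.2. A final statement that no related SAEs occurred would then say nothing about the return of results. Separately, the ethics committee is asked for a dispensation on a ground that the preceding section of the same protocol contradicts. The participants are minors, so both texts should be exact.

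**Working it through.** The point involves no rate, margin, power or sample-size figure, and the plan has no figure of its own to reproduce. The check is a comparison of sections.

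1. **Is returning results part of the study?** Yes. Section 7.3.2 sets out which results go back to cases and under what conditions. Section 7.3.1 collects the general practitioner's details for cases so that results can be fed back.

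2. **Does the protocol attach a risk to it?** Yes. Section 10.4 uses the word risk for a diagnosis without therapeutic consequences and says that it may burden the participant or family.

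3. **Can an SAE from disclosure meet the reporting rule?** No. Section 8.2.2 first speaks of SAEs related to participation, then narrows this to saliva collection and closes the list by excluding every other SAE. Section 8.2.1 registers no AEs.

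4. **Does another section supply a route?** Only in general terms. Section 11.4 lists serious adverse events and other problems among the contents of the annual progress report. Section 8.1 requires suspension and notification if subject health or safety is jeopardised. Neither sets up collection of events after disclosure, and neither is expedited. The counselling referral in 7.3.2 reduces harm, but no report back to the sponsor is described. That referral is written for likely IEI diagnoses, whereas incidental findings are returned as well.

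5. **Would rewording 8.2.2 be enough?** Not quite. Reporting ends at the end of the study (8.4), and the study ends when the last included participant's DNA results are received (11.5). A result can be disclosed only after it has been received. If the last participant is a case, or if any case's result is still to be returned on that day, the disclosure falls after the window has closed.

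6. **Is the ground for the dispensation consistent with 10.4?** No, on two counts. Section 10.4 names a risk from the diagnosis. It also rates saliva collection as negligible, which is not nil; section 12.2 uses the same rating for the kits.

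7. **How many children are concerned?** Cases only: 100 with MIS-C + 100 with post-COVID condition = at most 200. Only those who actually receive a result are exposed, and the documents do not say how many that will be.

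**The case against.** The best defence is that narrow SAE reporting is an explicit and reasoned choice in an observational study whose only physical procedure is a saliva sample. A burden is not in itself an SAE: 8.2.2 requires an untoward medical occurrence that meets a seriousness criterion. Counselling and the choices over incidental findings are real safeguards. Liability insurance stays in place, so only the separate subject insurance would be waived, and the committee reads 10.4 directly before 10.5. No endpoint, analysis or eligibility rule is affected.

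Most of this stands, and it keeps the point minor. It does not remove the contradiction. The choice in 8.2.2 is justified by the low risk of the saliva procedure and does not address the other procedure, for which 10.4 names a risk. Safeguards are not a reporting route. That the committee can read both sections does not make them agree.

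Several stronger readings are tempting but unsupported:

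- A reader might infer that harm from a result can never reach the ethics committee. Sections 11.4 and 8.1 leave general routes open; what is missing is a defined, expedited one.
- A reader might infer that the protocol regards this risk as a major one. Section 10.4 names a risk and a possible burden and does not grade them.
- A reader might take the 3/18 in section 3.4 as the scale of the problem. It is the share of patients with deleterious immunological variants in a previous MIS-C study. It is not a rate of harm after disclosure. Nor is it a safe upper limit on the results returned, because 7.3.2 also returns incidental and offspring-risk findings.
- A reader might say that none of these events would be captured. For expedited reporting that only restates the definition, since the number of events is unknown.

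**Conclusion.** The point holds as an internal contradiction of minor weight. Followed as written, 8.2.2 excludes from SAE reporting any event attributed to the return of a genetic result, although 7.3.2 makes that return a study procedure and 10.4 names a risk from it. The premise in 10.5 is inconsistent with 10.4. The SAE window set by 8.4 and 11.5 can also close before the last result is returned.

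The size is limited to cases, at most 200 and fewer in practice. The documents give no rate of disclosure-related SAEs; they may be rare, and none may occur. The conclusion rests on the text alone and assumes no event rate. It is not an argument for general AE registration.

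**What to change.** - **8.2.2:** define related SAEs as those arising *from the saliva collection or from the return of individual genetic results*, with the existing 7-day and 15-day times counted from the sponsor's first knowledge.
- **8.4 and 11.5:** reconcile them so that the SAE reporting window does not close before the last individual result has been returned.
- **7.3.2:** ask the counselling geneticist to notify the sponsor of such events. Extend the request to whoever returns incidental findings, because the referral text does not mention them.
- **10.5:** replace the statement that participation carries no risk with wording consistent with 10.4.
- **12.1 (optional):** list the return of results as an issue of concern.

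The cost is a few sentences and a small reporting duty for the sponsor and the counselling geneticist, with no new study visits. The ethics committee may look again at the insurance dispensation.

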8.3 Annual safety report

Not applicable.

8.4 Follow-up of adverse events

SAEs need to be reported till end of study within the Netherlands, as defined in the protocol

8.5 Data Safety Monitoring Board (DSMB)

Not applicable

9. STATISTICAL ANALYSIS

9.1 Primary study parameter(s)

The first steps in the analysis will be to **identify the qualifying variants**, as previously reviewed by Povysil *et al.* (40).

- 1) **Sample QC:** Obtained genotypes will be used to investigate the relatedness between samples. Samples that are too interrelated, possibly due to unknown relatedness, are excluded for further analysis as this violates the assumption of independence between samples. Likewise, samples that are too unrelated, possibly due to an unknown admixture, are excluded for further analysis as this would yield an inflated estimate of rare variants, that are in fact mostly benign population-specific variants.
- 2) **Variant QC:** For each contrast, variants are scrutinized for differences in coverage and other variant QC measures. Variants with significant differences in QC between cases and controls are discarded.
- 3) **Variant filtering:** This will enrich the subsequent gene-collapsing analyses for rare and presumably deleterious variation that confers disease risk, while minimizing the impact of neutral background variation. The goal is to optimize statistical power to test for involvement in the pathophysiology of MIS-C. For this purpose, we will filter for rare variation in external reference cohorts (gnomAD, MAF<0.00001). In addition, we will include only protein-altering variation with a presumed high impact on protein function, including protein-truncation (stop or frameshift mutations) or disturbance of canonical splice-sites. In-frame insertions/deletions and missense mutations will be scored, and variants with a 'likely' estimated impact on protein functioning (CADD>15) will be included in the analysis (37, 38).

Qualifying variant selection					
variant	gene	sample	filters		
			variant quality	variant annotation	external MAF
V1	G1	S1	ü	ü	ü
V1	G1	S2	û	ü	ü
V3	G2	S3	ü	ü	û
V4	G3	S3	ü	ü	ü
V5	G3	S4	ü	û	ü
V6	G4	S5	ü	ü	ü
...				...	
Vn	G453	S1	ü	ü	ü

[figure not shown]
Example of Qualifying Variant selection table, adapted from Povysil *et al.*, (40)

Cluster analysis of IEI gene-set

We have done a cluster analysis on the IEI-gene set. Leading Eigen cluster analysis was done based on known and predicted protein-protein interactions, using STRINGdb version 11.5 (41, 42). The interactions include direct (physical) and indirect (functional) associations. We included all interactions of medium confidence (cutoff = 0.4) and subsequently assigned

isolated genes to the best fitting cluster using label propagation. Enrichment of KEGG-pathways within these clusters was assessed using WebGestalt (43). A force-atlas graph algorithm was used for visualization.

Collapsing analysis of qualifying variants

All qualifying variants (QV) will be collapsed. The goal of collapsing is to optimize signal detection by reducing contamination from neutral background variation. Also, collapsing increases the power to answer our main question: “Do children with MIS-C or post-COVID condition have more deleterious variants in immunological genes than exposed controls?”

A cluster is affected in an individual if there is at least one gene with a QV.

Cluster	With affected gene(s)		Without affected gene(s)	
	cases	controls	cases	controls
C1	5	1	95	199
C2	1	2	99	198
C3	5	1	95	199
C4	1	1	99	199
C5	1	3	99	197

Gene	With QV		Without QV	
	cases	controls	cases	controls
G1	1	0	99	200
G2	0	1	100	199
G3	2	0	98	200
G4	0	0	100	200
G5	1	1	98	199
...				
G453	1	0	99	200

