3.4 Sample size calculation

Our study is powered to answer the main research question: "Do more children with MIS-C or post-COVID condition have deleterious variants in immunological genes than exposed controls?" To analyze the genetic data from the case-control study, we will use rare-variant collapsing analyses, as reviewed by Povysil, et al [35] (see Chapter 9 (Statistical Analysis) for details).

Power analysis using Monte Carlo simulation:

In a previous study in MIS-C, 17% of patients (3/18) had deleterious variants in immunological genes. In controls, the prevalence of (predicted) loss of function variants in our gene-set is about 3.7% (according to gnomAD v. 2.1.1 data, using a minor allele frequency of <0.00001). This yields an odds ratio of 5.2 ($3/18 * 0.963 / (0.037 * 15/18)$). **Therefore, for the power analysis, we conservatively assume that cases have more qualifying variants than healthy controls, with an odds ratio of 4.** We found the 'normal variation' in controls to be present in all the clusters. We assume that the 'background variation' in cases is similarly spread out over the clusters.

The simulations have been run 1000x, with 100 cases and 200 controls.

Causative variants should cluster together

We hypothesize that causative genetic variants that are more prevalent in cases are functionally related. They underly a pathogenic mechanism and should cluster together. Therefore, we assume that excess variants in cases cluster together, either in one or in two clusters. See Chapter 9 (Statistical Analysis) for details on the cluster analysis.

Power of 80% assuming an odds ratio of 4 and one cluster affected

Individuals are positive if they have at least one qualifying variant in at least one gene. The **overall positive rate** is the proportion of simulations in which the Fisher exact P value comparing positive cases and controls is <0.05 . A genecluster-by-individual collapsing matrix is constructed. For every simulated case or control it is assessed if at least one of the clusters is affected. A Fisher exact test is calculated for each simulation. The **cluster true positive rate** is the proportion of simulations in which both the overall Fisher exact P-value and the cluster-specific Q-value (using Benjamini-Hochberg FDR) are <0.05 .

Cluster	Overall positive rate	Cluster true positive rate	Cluster false positive rate
1	0.823	0.807	0.014
2	0.814	0.791	0.008
3	0.812	0.803	0.014
4	0.833	0.816	0.012
5	0.806	0.772	0.002

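### The rarity rule in 9.1 rests on one gnomAD cutoff; GoNL has no cutoff and no within-study limit is stated, so recurrent variants that gnomAD lacks can qualify and dilute the effect

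*Protocol*

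**What the plan says.** Section 9.1 (Variant filtering) sets the frequency condition for a qualifying variant: "we will filter for rare variation in external reference cohorts (gnomAD, MAF<0.00001"). The example selection table in the same section has three filter columns: variant quality, variant annotation and external MAF. None of them concerns frequency among the study's own samples.

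Section 7.3.2 is wider. It plans to use "publicly available reference exome data sets (including GnomAD database, GoNL database) to determine the frequency of genetic variants in reference populations". It states no cutoff for GoNL.

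Section 9.1 gives the purpose of the filter as enriching for deleterious variation "while minimizing the impact of neutral background variation".

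Three guards in 9.1 bear on the same problem:
- a per-variant quality filter;
- a comparison between groups: "Variants with significant differences in QC between cases and controls are discarded";
- a sample-level rule: "samples that are too unrelated, possibly due to an unknown admixture, are excluded for further analysis", because such samples would inflate the count with variants that are "mostly benign population-specific variants".

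**The concern.** A filter based only on an external reference treats absence from that reference as evidence of rarity. Two kinds of variant can be absent from gnomAD and yet be common in this study: a benign variant concentrated in the local population, and a systematic call produced by this study's capture kit or pipeline. Either could appear in several of the 400 exomes and still pass 9.1.

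The guards leave a gap. The quality filter should catch some artefacts, but not a real, well-called local variant. The case-control QC comparison removes variants whose quality differs between groups, so an artefact equally common in both passes. Excluding outlying samples deals with children of unusual ancestry, but a local variant in a child who is not an outlier stays in.

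The main stake is power. Equal contamination raises the carrier rate in both groups and pulls the odds ratio towards 1, which works against the filter's stated purpose. The two sections also differ on which reference sets define the variable that the primary comparison counts.

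**Working it through.** **Inputs from Section 3.4**
- Control carrier rate p0 = 0.037: "the prevalence of (predicted) loss of function variants in our gene-set is about 3.7" per cent.
- Odds ratio 4; 100 cases and 200 controls; Fisher exact test at 0.05. Sidedness is not stated, so two-sided is assumed.

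**Step 1: reproduce the plan's power.**
Odds in controls = 0.037/0.963 = 0.03842. Odds in cases = 4 × 0.03842 = 0.15369. Case rate p1 = 0.15369/1.15369 = 0.1332.

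Enumerating both binomials and summing the probability of all tables with a two-sided Fisher P < 0.05 gives power 0.826. Section 3.4 reports overall positive rates of 0.806 to 0.833 (one cluster affected) and 0.809 to 0.844 (two clusters). The plan's figure is right on its own inputs.

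**Step 2: add non-causal carriers equally to both groups.**
Let b be the share of children carrying a non-causal variant that passes the filter, independently of true carrier status. Each rate p becomes 1 − (1 − p)(1 − b). For b = 0.01: controls 1 − 0.963 × 0.99 = 0.0466; cases 1 − 0.8668 × 0.99 = 0.1419.

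| b (assumed) | Controls | Cases | Odds ratio | Exact power |
|---|---|---|---|---|
| 0 | 0.0370 | 0.1332 | 4.00 | 0.826 |
| 0.5% | 0.0418 | 0.1375 | 3.65 | 0.800 |
| 1% | 0.0466 | 0.1419 | 3.38 | 0.773 |
| 2% | 0.0563 | 0.1505 | 2.97 | 0.721 |
| 5% | 0.0852 | 0.1766 | 2.30 | 0.594 |

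At b = 0.5% the expected number of extra carriers among the 300 children in one comparison is 0.005 × 300 = 1.5, and power is already down to 0.80.

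**Step 3: what an internal cap would cost in truly rare variants.**
The 400 exomes carry 800 alleles. A variant with a population frequency of 0.00001 has 800 × 0.00001 = 0.008 expected copies. With a Poisson mean of 0.008, P(3 or more) = 8.5 × 10⁻⁸ and P(2 or more) = 3.2 × 10⁻⁵. Three heterozygous carriers give an observed frequency of 3/800 = 0.00375, which is 375 times the stated cutoff. These probabilities apply to a variant unrelated to disease. They do not apply to a risk variant, which the case sampling enriches.

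**Step 4: why GoNL needs its own cutoff.**
In a set of N alleles the smallest non-zero frequency is 1/N. A cutoff of 0.00001 can therefore be told apart from zero only if N exceeds 1/0.00001 = 100,000 alleles. The documents do not give GoNL's size. In a set smaller than that, the gnomAD cutoff would amount to requiring complete absence.

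**The case against.** **GoNL is not ignored.** Section 7.3.2 names it as a frequency source, and 9.1 speaks of reference cohorts in the plural. This stands: a reader might infer that GoNL is left out of the study altogether, and the documents do not support that. What remains is that GoNL has no cutoff and is missing from the operative rule.

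**A recurrence cap is a pipeline detail for the SAP.** This is partly right, and the missing cap alone would be a weak point. But the protocol itself fixes the source, the cutoff and the filter columns, and its two sections do not match.

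**The guards count for something.** They do. The quality filter should remove some artefacts, and excluding outlying samples should remove some population-specific variants. No document shows how many would get through.

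**The size is assumed, and the baseline is narrow.** Both hold. The documents give no value for b. The 3.7% covers predicted loss-of-function variants only, while the 9.1 filter also admits in-frame indels and missense variants with CADD>15, so the table describes the power calculation rather than the full analysis. Section 3.4 also presents odds ratio 4 as conservative against 5.2. With a case rate of 3/18, the same calculation gives power 0.955, and 0.930, 0.902 and 0.814 at b = 1%, 2% and 5%. A reader might infer that a few recurrent variants would erase the signal. That does not follow: even at b = 5% with odds ratio 4, the diluted odds ratio is 2.30 and power 0.594.

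**A cap could delete the signal.** A risk variant seen in three cases and no controls would be dropped. Nor does a cap at three touch variants seen once or twice, so it would not remove all of b. Both points stand and shape the fix.

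**Conclusion.** The point holds as a gap in the filter definition with a cost in power. Section 9.1 as written lets a variant that gnomAD lacks qualify however often it recurs in the study, Section 7.3.2 names a second reference set that the rule does not use, and the guards close only part of the gap.

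On the protocol's power inputs, 0.5% to 5% of children carrying such variants would lower power from 0.826 to between 0.800 and 0.594. This assumes that the share is equal in both groups, that these carriers are independent of true carriers, and that the Fisher test is two-sided. The share itself is unknown. With odds ratio 4 there is little slack above 80%; with 5.2 there is much more.

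A reader might also infer a false-positive problem. Contamination that is equal in both groups does not bias the test under the null, so the documents do not support that reading for the mechanism described here.

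**What to change.** In 9.1:
1. State that the frequency filter uses both gnomAD and GoNL, with a cutoff for each that suits the size of the set, and make 7.3.2 say the same.
2. Add a prespecified internal cap, for example dropping any variant seen in 3 or more of the 400 unrelated exomes, counted over all groups pooled and blind to case status.
3. List the recurrent variants removed by the cap separately, with their counts by group.
4. Repeat the collapsed test without the cap as a sensitivity analysis.

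The cost is a few lines of text, one extra filter step and one repeat analysis, with no new data. The cap loses almost no truly rare variants unrelated to disease (Step 3). Its real downside is that a genuinely recurrent risk variant would leave the main collapsed test; items 3 and 4 keep it visible. Variants seen once or twice are unaffected, so power returns at most to the planned 0.826. The rule should be fixed before case status is joined to the variant data.
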